# **Protocol Amendment Summary of Changes Table**

| DOCUMENT HISTORY  |               |  |
|-------------------|---------------|--|
| Document          | Date          |  |
| Amendment 2       | May 10, 2021  |  |
| Amendment 1       | January 2020  |  |
| Original Protocol | November 2019 |  |

#### Amendment 2 (May 10. 2021)

#### **Overall Rationale for the Amendment:**

Interim analysis may be performed; minor edits.

| Section # and Name | Description of Change                                 | Brief Rationale                                   |
|--------------------|---|---|
| Title Page         | Added Regulatory Agency                               | As assigned.                                      |
|                    | Identifying Numbers                                   |   |
|                    |   |   |
| Appendix 8         | Moved Rationale/Summary of
Changes for Amendment 1 | Added Rationale/Summary of
Changes Amendment 2 |

| Endpoints   |
|---|
| • Primary: Responder status based on the evaluating investigator's (EI) live assessment of temple hollowing using the Allergan Temple Hollowing Scale (ATHS) at Month 3   |
| • Secondary: Responder status based on EI assessments of global aesthetic improvement in the temple area using the Global Aesthetic Improvement Scale (GAIS) at Month 3   |
| • Secondary: Responder status based on participant assessments of global aesthetic improvement in the temple area using the GAIS at Month 3   |
| • Secondary: Change from baseline on FACE-Q Satisfaction with Facial Appearance questionnaire at Month 3  |
| • Secondary: Change from baseline on FACE-Q Satisfaction with Temples questionnaire at Month 3  |
| 
 
Participant assessment of procedural pain
 
Participant assessment of injection site responses
 
Adverse events
 
Jaw Functional Limitation Scale
 
Vision Assessments: 
 
Snellen visual acuity
 
confrontational visual fields
 
ocular motility
 
 
 
Concomitant medication and procedures
 
 |
|   |

#### **Overall Study Design:**

- Multicenter, randomized, controlled, parallel-design study in participants with minimal, moderate, or severe temple hollowing (Grade 2, 3, or 4 on the ATHS)
- Single-blind: EIs are blinded; treating investigators (TIs) and participants are not blinded
- VOLUMA XC injected with 27 G 1/2" or 25 G 1" needles to the supraperiosteal plane in the temple area (up to 6 mL for initial and touch-up treatments combined) for the treatment group and delayed treatment for the control group

#### Number of Participants:

Up to 213 participants will be enrolled and screened to achieve 171 randomized (114 treatment group, 57 control group) and 135 evaluable participants (90 treatment group, 45 control group) at the Month 3 primary timepoint.

#### Number of Sites:

Up to 15 North American sites

[figure not shown]
#### **Intervention Groups and Study Duration:**

• Participants will be randomized on study intervention day in a 2:1 ratio of treatment group to control group. Screening period is up to 30 days for all participants.

Protocol 1878-702-008 Amendment 2

#### 1.3. Schedule of Activities

#### Table 1-1

#### Screening Visit Procedures: All Participants

| Procedure   | Screening |
|---|-----------|
| Visit Window (Days)                                 | -30       |
| Consent/authorization                               | Х         |
| Participant demographics                            | Х         |
| Height, weight, and vital signs a        | Х         |
| Fitzpatrick skin phototype and sun exposure history | Х         |
| Smoking and tobacco use history                     | Х         |
| Medical/surgical/cosmetic/dental history            | Х         |
| Urine pregnancy test b                   | Х         |
| ATHS (EI)   | Х         |
| Inclusion/exclusion criteria (TI) c      | Х         |
| Adverse events                                      | Х         |
| Concomitant medications, procedures, therapies      | Х         |

a Includes blood pressure (systolic and diastolic; while participant is seated), pulse rate, and temperature.

b For female participants of childbearing potential; administered and confirmed negative prior to study intervention.
 A female is not considered of childbearing potential if she has been postmenopausal for at least 1 year or does not have a uterus at the time of study entry.

c TI will use EI ATHS scores to confirm participant's eligibility in the study.

#### CONFIDENTIAL JUVÉDERM VOLUMA® XC injectable gel

Protocol 1878-702-008 Amendment 2

| Table 1-2         Treatment Group Procedures: Treatment Period          |  |                         |                          |  |                          |                           |
|---|--|-------------------------|--------------------------|--|--------------------------|---------------------------|
| Procedure   |  |                         | Initial                  |  |                          | սթ                        |
|   | Randomization a /Initial Tx | 3 Days After Initial Tx | 14 Days After Initial Tx | 30 Days After Initial Tx /
Touch-up Tx b | 3 Days After Touch-up Tx | 14 Days After Touch-up Tx |
| Visit Window (Days)   |  | ±2                      | +4                       | + 10   | ± 2                      | +4                        |
| Urine pregnancy test c                                       | Xď                                     |                         |                          | Xe   |                          |                           |
| ATHS (EI) f  | Xď                                     |                         |                          |  |                          |                           |
| Inclusion/exclusion criteria (TI)                                       | Xď                                     |                         |                          |  |                          |                           |
| 3D facial digital imaging   | Xď                                     |                         | Х                        | Xe   |                          | Х                         |
| FACE-Q (Participant)  |  |                         |                          |  |                          |                           |
| 
 
Satisfaction with Facial Appearance
 
                 | Xď                                     |                         |                          |  |                          |                           |
| Satisfaction with Temples   |  |                         |                          |  |                          |                           |
| Self-perception of age (Participant)                                    | Xď                                     |                         |                          |  |                          |                           |
| Jaw Functional Limitation Scale (Participant)                           | Xď                                     |                         | Х                        | Х  |                          | Х                         |
| Randomization e  | Х                                      |                         |                          |  |                          |                           |
| Vision Assessments: (TI or designee)                                    |  |                         |                          |  |                          |                           |
| Snellen visual acuity   | Xg                                     |                         | x                        | Xg   |                          | x                         |
| 
 
Confrontational visual fields
 
                       | A                                      |                         | Λ                        | Л  |                          | Λ                         |
| Ocular motility   |  |                         |                          |  |                          |                           |
| Study intervention, intervention characteristics (TI)                   | Х                                      |                         |                          | Χ  |                          |                           |
| Injection ease and product moldability (TI)                             | Х                                      |                         |                          | Χ  |                          |                           |
| Procedural pain (Participant)   | Х                                      |                         |                          | Χ  |                          |                           |
| Safety telephone call   |  | Х                       |                          |  | Χ                        |                           |
| Safety e-diary h (Participant)                               | Con                                    | tinuo                   | ous                      | Con  | tinuo                    | ous                       |
| Adverse events i (TI)  | Co                                     | ontin                   | lous                     | moni   | torin                    | ıg                        |
| Concomitant medications and concurrent procedures (TI) Continuous monit |  | torin                   | g                        |  |                          |                           |

Tx = treatment

a Randomization must occur within 30 days of screening; screening visit and randomization visit can occur on the same day if participants do not require washout. If screening and randomization visits occur on the same day, inclusion/exclusion criteria, ATHS, and urine pregnancy test need not be repeated.

c For female participants of childbearing potential; administered and confirmed negative prior to study intervention. A female is not considered of childbearing potential if she has been postmenopausal for at least 1 year or does not have a uterus at the time of study entry.

d Done prior to randomization and study intervention.

e Done prior to study intervention.

- f TI will use EI ATHS scores to confirm participant's eligibility in the study.
- g On initial and touch-up treatment days, vision assessments will be performed by TI (or designee) before study intervention and at least 30 minutes after completing last injection procedure.
- h The safety e-diaries are to be completed following each study intervention starting on the day of treatment.

#### CONFIDENTIAL JUVÉDERM VOLUMA® XC injectable gel

Table 1-3

#### **Treatment Group Procedures: Follow-up Period**

| Procedure  | Procedure Follow-up a |         |             |          |   |
|--|----------------------------------|---------|-------------|----------|---|
|  | Month 1                          | Month 3 | Month 6     | Month 9  | Month 13 b
/Exit Visit c |
| Visit Window (Days)  | + 10                             | ± 7     | ±15         | ± 7      | ±15   |
| Urine pregnancy test d  |                                  |         |             |          | Х   |
| Weight   |                                  | Х       |             |          | Х   |
| 3D facial digital imaging  | Х                                | Х       | Х           |          | Х   |
| FACE-Q (Participant):  |                                  |         |             |          |   |
| 

Satisfaction with Facial Appearance

Satisfaction with Temples

  | х                                | Х       | Х           |          | Х   |
| Jaw Functional Limitation Scale (Participant)  | Х                                |         |             |          |   |
| Treatment Satisfaction Questions (Participant):  |                                  |         |             |          |   |
| 
 
Satisfaction with treatment
 
Natural look and feel of the results
 
How treatment met expectation
 
Likelihood of continuing the treatment
 
Willingness to recommend treatment
 
 |                                  | х       | х           |          | Х   |
| Self-perception of age (Participant)   |                                  | Х       | Х           |          | Х   |
| GAIS (Participant)   | Х                                | Х       | Х           |          | Х   |
| ATHS (EI)  | Х                                | Х       | Х           |          | Х   |
| GAIS (EI)  | Х                                | Х       | Х           |          | Х   |
| Vision Assessments: (TI or designee) 
 
Snellen visual acuity
 
Confrontational visual fields
 
Ocular motility
 
   | х                                |         |             |          |   |
| Safety telephone call  |                                  |         |             | Х        |   |
| Reason for not receiving maintenance (Participant)   |                                  |         |             |          | Х   |
| Adverse events e (TI)   |                                  | Con     | tinuous mor | nitoring |   |
| Concomitant medications and concurrent procedures
(TI)  | Continuous monitoring            |         |             |          |   |

a month = 30 days

a The follow-up visit schedule is based on the date of the last study intervention (ie, if no touch-up treatment is performed, the Month 1 visit occurs 30 days after initial treatment; if touch-up treatment is performed, the Month 1 visit occurs 30 days after touch-up treatment).

b At the Month 13 visit, participants will be offered a maintenance treatment after completion of the Month 13 visit. Participants who accept maintenance treatment will undergo the additional procedures specified in Table 1-4. Participants who do not accept maintenance treatment will exit the study after the Month 13 procedures are completed.

c If a participant withdraws for any reason prior to the final study visit, attempts will be made to perform assessments at an exit visit.

d For female participants of childbearing potential. A female is not considered of childbearing potential if she has been postmenopausal for at least 1 year or does not have a uterus at the time of study entry.

e Will include a general, nondirected question about vision symptoms.

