| Adverse events (TI)                                      | Continuous monitoring             |                        |                                     |  |
| Concomitant medications and concurrent procedures (TI)   | Continuous monitoring             |                        |                                     |  |

a month = 30 days

a Randomization must occur within 30 days of screening; screening visit and randomization visit can occur on the same day if participants do not require washout. If screening and randomization visits occur on the same day, inclusion/exclusion criteria, ATHS, and urine pregnancy test need not be repeated.

b During the control period, all follow-up visits are scheduled from the date of randomization.

c At the Month 3 visit, the TI will discuss the option for the control group participant to receive study intervention. Participants who accept optional treatment, after completing the procedures under Month 3, will undergo the additional procedures specified in Table 1-6. Participants who do not accept optional treatment will exit the study after the Month 3 procedures are completed.

d For female participants of childbearing potential. A female is not considered of childbearing potential if she has been postmenopausal for at least 1 year or does not have a uterus at the time of study entry.

e TI will use EI ATHS scores to confirm participant's eligibility in the study.

f Done prior to randomization.

Protocol 1878-702-008 Amendment 2

Table 1-6

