### 10.7.1. Definition of AE, ADE, and AESI

### AE and ADE Definition

- An AE is defined as any untoward medical occurrence, unintended disease or injury, or untoward clinical signs (including abnormal laboratory finding) in study participants, users, or other persons, whether or not related to the investigational medical device. This definition includes events related to the investigational medical device or comparator and events related to the procedures involved except for events in users or other persons, which only include events related to investigational devices.
- An ADE is defined as an adverse event related to the use of an investigational medical device. This definition includes any adverse events resulting from insufficient or inadequate instructions for use, deployment, implantation, installation, or operation, or any malfunction of the investigational medical device as well as any event resulting from use error or from intentional misuse of the investigational medical device.
- An AESI (serious or non-serious) is one of scientific and medical concern specific to the sponsor's study device, which warrants ongoing monitoring and rapid communication by the PI to the sponsor. Such an event might warrant further investigation in order to characterize and understand it. The following AESIs have been identified for the study intervention in this protocol: any incidence of visual disturbance (including, but not limited to, any loss of vision, blurry vision, double vision, pain in or around eye [excluding pain in temple area], blind spot or shadow in the visual field, trouble moving eyes, etc.).

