4.0 Analysis Populations

The analysis populations will consist of participants as defined in Table 1 below:

Table 1. Analysis Sets

Population	Definition	Study Intervention
mITT	All randomized participants who have non-missing baseline assessment on the AHS for both temples. This will be used as the full-analysis-set population.	As randomized
Observed Primary Endpoint (OPE)	All mITT population participants who have a Month 3 assessment on the AHS for both temples.	As randomized
Safety	All participants who are randomized and received study intervention (VOLUMA XC or no-treatment control).	As treated
VOLUMA XC Treated (VT)	All safety population participants who received VOLUMA XC treatment as initial treatment at the beginning of the Control Period, or as optional treatment after the Control Period	As treated
VOLUMA XC Maintenance Treatment (VMT)	All safety population participants who received VOLUMA XC maintenance treatment	As treated

The number of participants in each of the 5 study populations (mITT, OPE, Safety, VT and VMT) will be summarized by treatment group, if applicable.

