9.2.2 Adverse Event Overview

TEAEs will be summarized by treatment group for CP using the safety population. TEAEs will also be summarized by treatment group for TP and MP using the VT and VMT populations, respectively as described in Table 9. The summaries will be presented using number and percentage of participants with TEAEs as well as the number of events. Additional summaries may be provided when applicable.

An overall summary of TEAEs will be presented as described in Table 9.

Treatment-related AEs will be summarized by duration, severity, time to onset on/after the most recent treatment, and outcome.

The duration of an AE is defined as the end date of AE minus the start date of AE plus 1.

For participants who received maintenance treatment, their AEs reported during the first 6 months from the initial treatment will be summarized and presented in parallel with AEs reported during the maintenance treatment period. The summary for the initial treatment will be presented for participants who received initial treatment only and participants who received both initial and touch-up treatments.

If more than 1 AE is coded to the same preferred term for a participant, the participant will be counted only once for that preferred term using the most severe and most related occurrence for the severity and relationship to study intervention summaries, respectively.

If the severity of a TEAE is missing, the maximum severity will be assigned to the event for the summary on severity. The value will be displayed as missing in the data listing.

If the relationship to the study intervention is missing for a TEAE, the event will be considered related to the study intervention for the summary. The value will be displayed as missing in the data listing.

Listings of all AEs, TESAEs, TEAEs leading to discontinuation, and death will be presented.

Table 9. TEAE Summaries

Endpoint	Description	Timing	Methodology
Overall summary	Overall summary only for the following categories: 
 • TEAEs • Treatment-related TEAEs • Treatment-related TEAEs at injection site • Treatment-related TEAEs not at injection site • TESAEs • Treatment-related TESAEs • Treatment-related TESAEs at injection site • Treatment-related TESAEs not at injection site • Discontinued due to TEAEs • AESIs • Treatment-related AESIs • Deaths • TEAEs related to COVID-19 infection 	CP, TP, MP	Frequency counts and percentages

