9.2.3 Adverse Events of Special Interest

The following AESIs have been identified for the study intervention in this study: visual disturbance (including, but not limited to, any loss of vision, vision, double vision, pain in

or around eye [excluding pain in temple area], blind spot or shadow in the visual field, trouble moving eyes, etc.).

The incidence of AESIs will be summarized by SOC and PT and listed in a separate listing.

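### In the visible schedule, the vision-symptom question is put to treated participants but not to untreated controls during the control period, so the by-arm AESI columns in SAP Table 9 rest on unequal elicitation

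*Protocol*

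**What the plan says.** Protocol 10.7.1 names one AESI, "any incidence of visual disturbance (including, but not limited to, any loss of vision, blurry vision, double vision" and further eye complaints. Most of the listed examples are symptoms that the participant has to report.

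The schedules of activities deal with the adverse-event row as follows.

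- **Table 1-3 (treatment group, follow-up).** The row begins "Adverse events e (TI", and footnote e reads "Will include a general, nondirected question about vision symptoms".
- **Tables 1-4 (maintenance) and 1-6 (controls after optional treatment).** The row carries footnotes i and j respectively, with the same text.
- **Table 1-2 (treatment group, treatment period).** The row begins "Adverse events i (TI". The marker is there, but the text of footnote i is not visible in the public document.
- **Table 1-5 (untreated control period).** The row begins "Adverse events (TI", with no marker. Footnotes a to f are all present and none mentions vision.

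On analysis, SAP 9.2.2 states "TEAEs will be summarized by treatment group for CP using the safety population". The SAP 4.0 definition of that population is "All participants who are randomized and received study intervention (VOLUMA XC or no-treatment control", followed by a closing bracket, so untreated controls are included. AESIs and treatment-related AESIs are lines in the Table 9 overall summary, with timing CP (control period), TP and MP. SAP 9.2.3 adds "The incidence of AESIs will be summarized by SOC and PT and listed in a separate listing".

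**The concern.** The untreated controls are the trial's only concurrent source for how often blurry vision, eye pain and similar complaints arise without an injection. If one arm is prompted about vision and the other is not, the two control-period AESI columns differ in how events are found as well as in exposure. A gap between them can then appear with no device effect at all. Equal follow-up time would not remove it, because the gap comes from asking and not from time at risk.

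The question follows exposure within the same people: a control is not asked at Months 1 and 3 of the control period, but is asked after accepting optional treatment. Participants and treating investigators are unblinded, and the treating investigator records adverse events, so nothing else in the visible design offsets the difference.

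**Working it through.** **Step 1. Do the treated arm's Month 1 and Month 3 visits fall in the control period?** Yes. SAP Table 2 runs the control period for the VOLUMA XC group from initial treatment to the Month 3 assessment, and Table 1-3 schedules both visits. Comparing Table 1-3 with Table 1-5 is enough for the finding; Table 1-2 is not needed.

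**Step 2. What each arm receives in the control period, from the visible tables.**

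| Route to a visual AESI | Treatment group | Control group |
|---|---|---|
| Continuous adverse-event monitoring | Yes | Yes |
| Vision-symptom question at Months 1 and 3 | Yes (Table 1-3, footnote e) | Not scheduled (Table 1-5) |
| Acuity, visual fields, ocular motility | Treatment days, Day 14 after each treatment, Month 1 | None |
| Safety telephone call | Day 3 after each treatment | None |
| Scheduled contacts after baseline | 4 without touch-up (Day 3, Day 14, Day 30 = Month 1, Month 3); 7 with touch-up | 2 (Months 1 and 3) |

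**Step 3. Size of the distortion.** The plan states no AESI rate and no capture probability, so there is no figure of its own to reproduce. The following is an illustration under stated assumptions.

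Inputs: 114 treated and 57 controls randomized (Protocol, Number of Participants). Assumed: the same true background rate p in both arms and no device effect; capture of 100% with the question; capture c of 30% to 70% without it.

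- Spurious excess = p × (1 − c), so from 0.3p (c = 70%) to 0.7p (c = 30%).
- Expected treated count = 114p. Expected control count = 57p if asked, 57pc if not.
- Chance of no AESI among 57 controls = (1 − p)^57 if asked, (1 − pc)^57 if not.

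| Assumed p | Treated count | Control count, asked | Control count, not asked | Spurious excess (points) | P(zero controls), asked | P(zero controls), not asked |
|---|---|---|---|---|---|---|
| 1% | 1.1 | 0.6 | 0.2–0.4 | 0.3–0.7 | 56% | 67–84% |
| 2% | 2.3 | 1.1 | 0.3–0.8 | 0.6–1.4 | 32% | 45–71% |
| 5% | 5.7 | 2.9 | 0.9–2.0 | 1.5–3.5 | 5% | 13–42% |
| 10% | 11.4 | 5.7 | 1.7–4.0 | 3.0–7.0 | 0.2% | 2–18% |

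Example at p = 5%: 5 × (1 − 0.7) = 1.5 points and 5 × (1 − 0.3) = 3.5 points; 0.95^57 = 0.054, 0.965^57 = 0.131, 0.985^57 = 0.42.

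With equal capture (c = 100%) the excess is zero at every p.

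**The case against.** Several points on the other side stand.

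- **Hidden text.** Protocol 8.2 is largely not shown and 8.3 does not appear in the public text. How adverse events are elicited would normally be described there, so a general instruction to ask every participant cannot be excluded. If there is one, Table 1-5 still differs from the other schedules and needs aligning.
- **Reach of the footnote.** A reader might infer that every treated schedule carries the question. The documents show it in three of four; for Table 1-2 only the marker is visible.
- **Not absent collection.** A reader might also infer that control AESIs are not collected. They are: Table 1-5 requires continuous monitoring. What differs is the prompting.
- **No test.** Table 9 gives counts and percentages, and the testing sequence in SAP 12.0 covers only the ATHS responder endpoint and the two FACE-Q scales. AESIs are also listed individually and assessed for causality, so it would be too much to say that a device effect could not be judged at all.
- **Direction.** Asking controls less inflates the apparent device excess. It does not hide a signal in the treated arm, and a reading that safety is being masked has no support in the documents.
- **Low rates.** Exclusions 1.09, 1.14 and 2.10 remove several eye conditions and recent eye surgery, so the 1% and 2% rows may be the relevant ones. At 1%, the control column would be empty 56% of the time even if every control were asked.

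These points limit the consequence. They do not remove the mismatch between the visible schedule and a display that places the arms side by side.

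**Conclusion.** The point holds in a limited form. On the visible schedule, elicitation of the only AESI is unequal during the control period, and SAP Table 9 shows that AESI by arm for the same period. No text in the visible documents acknowledges or adjusts for this. The likely result is a control background rate that is too low and a device excess that looks too high: about 0.3–0.7 percentage points at a 1% background, rising to 3–7 at 10%. Those figures rest wholly on assumed background rates, on full capture with the question and on 30–70% capture without it. The consequence is for the interpretation of a descriptive safety table. It does not affect the primary endpoint or any hypothesis test.

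**What to change.** Two changes, both small.

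1. **Protocol Table 1-5.** Attach to the adverse-event row the vision-symptom footnote already used in Tables 1-3, 1-4 and 1-6, so that controls are asked at Month 1 and Month 3 in the same words as the treated arm. This adds one question at two visits that already take place. The downside is a few more visual complaints in controls that are unrelated to the device, each of which needs AESI reporting.

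2. **SAP Table 9, control-period AESI lines.** The question alone does not equalize ascertainment, because treated participants also have vision examinations and safety calls. Add a note that ascertainment of visual disturbance differs by arm and that the columns are not to be read as a between-arm comparison. The cost is one table note.

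The documents do not say whether control visits are finished. SAP version 3.0 (September 2021) refers to a validation analysis of the study's own baseline data (Appendix F-2), and its version history says the interim efficacy analysis includes visits up to Month 6, so the first change may come too late. If control visits are complete, the note alone applies.
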